4.1.5 Statistical modelling

In general, continuous variables will be analyzed using a MMRM if multiple post-baseline measurements are required by CSP. The MMRM analysis will be treated as the primary analysis method for continuous efficacy endpoints. The statistical analysis of categorical variables will be done using a stratified Cochran-Mantel-Haenszel (CMH) test.

Standard diagnostic approaches will be used to verify that the key statistical assumptions of the MMRM and CMH test hold.

If the distributional assumptions of the MMRM for the primary analysis do not hold, alternative models will be explored using appropriate transformed data.

4.2 Analysis methods

4.2.1 Study disposition and baseline demographics

4.2.1.1 Patient disposition

Patient disposition information for all patients who provided informed consent, including counts and percentages of patients who completed the controlled assessment period and extension period will be summarized. Patients who discontinue study medication early and patients who discontinue the study early (including reasons for early discontinuation) during the controlled assessment and extension periods, will be summarized overall and by region and country for each treatment group, for all patients. The denominator for percentages will be the total number of patients in the randomized analysis set, overall and by treatment group. No percentage will be displayed for number of patients enrolled. A listing of patient disposition will be provided, including reasons for early discontinuation and reasons for IP discontinuation. A flow diagram of patient disposition will be presented.

The number and percentage of patients in each analysis set will also be reported overall and by treatment group. The denominator for percentages will be the total number of patients in the randomized analysis set, overall and by treatment group.

4.2.1.2 Demographics and baseline characteristics

Demographic and baseline characteristics will be summarized for the ITT and safety analysis sets overall and by treatment group as per below table.

Table 1 Analysis for demographics, baseline patient and disease characteristics

Demographic and baseline characteristics	Categories
Age (years), (continuous)	

Table 1 Analysis for demographics, baseline patient and disease characteristics

Demographic and baseline characteristics	Categories
Age group 1 (years), (categorical)	<10
	10 to 17
	>17
Age group 2 (years), (categorical)	<10
	10 to 12
	13 to 16
	> 16
Sex	Male
	Female
Race	White
	Black or African American
	Asian
	Native Hawaiian or Other Pacific Islander
	American Indian or Alaska Native
	Other
Ethnic Group	Hispanic or Latino
	Not Hispanic or Latino
Region	Europe
	Middle East
	North America
	South America
Country	Bulgaria
	Hungary
	Israel
	Mexico
	Ukraine
	USA
	Kuwait
Height (cm), (continuous)	

Table 1 Analysis for demographics, baseline patient and disease characteristics

Demographic and baseline characteristics	Categories
Weight (kg), (continuous)	
Body Mass Index (BMI) (kg/m ²), (continuous)	
Height population percentile group (categorical)	<3 3 to < 85 85 to < 97 > = 97
Weight population percentile group (categorical)	<3 3 to < 85 85 to < 97 > = 97
BMI population percentile group (categorical)	<3 3 to < 85 85 to < 97 > = 97
Baseline HbA1c (%), (continuous)	
HbA1c stratum (%), (categorical)	<9.0 ≥9.0
Duration of Diabetes (years), (continuous)	
Duration of Diabetes (years), (categorical)	< 1 ≥ 1 to ≤5 >5
Baseline FPG (fasting plasma glucose), mg/dL, (continuous)	
Baseline FPG (fasting plasma glucose), mmol/L, (continuous)	
Baseline eGFR (mL/min/1.73 ²) (continuous)	
Baseline eGFR (mL/min/1.73 ²)	≥125 <125

Table 1 Analysis for demographics, baseline patient and disease characteristics

Demographic and baseline characteristics	Categories
Baseline Tanner Stage	Stage 1 Stage 2 Stage 3 Stage 4 Stage 5

Patient's age (years) will be presented as collected on the DM eCRF at screening.

BMI will be calculated as the ratio of patient's baseline weight (in kilograms) to the square of the patient's height (in meters): $BMI = \text{kg}/\text{m}^2$. The Investigator-calculated BMI will not be summarized or listed. Height is collected in cm and will be converted to meters (by dividing by 100) before calculating BMI.

Percentile of body weight and percentile of height will be determined based on the standardized growth chart for boys and girls (developed by the National Center for Health Statistics in collaboration with the National Center for Chronic Disease Prevention and Health Promotion (Center for Disease Control and Prevention, 2000)).

Duration of diabetes (years) will be calculated using the informed consent date and the date of diabetes diagnosis (see below).

If date of diabetes diagnosis is...	Then duration of diabetes (years) is...
Complete date	$(\text{Date of informed consent} - \text{Date of diabetes diagnosis} + 1) / 365.25$
Partial date (a) Year and month are not missing, but day is missing (b) Year is not missing, but month and date are both missing (b1) Year of diabetes diagnosis is different from the year of informed consent (b2) Year of diabetes diagnosis is the same as year of informed consent	(a) Impute missing day 1 st of the month, then use complete date rule (b1) Difference between year of diabetes diagnosis and year of informed consent (b2) 2/12 (2 months)

4.2.1.3 Medical/Surgical history

All medical/surgical history by each system organ class (SOC) and preferred term (PT) will be summarized by treatment group for the safety analysis set in accordance with the terminology

of the latest version of the Medical Dictionary for Regulatory Activities (MedDRA) available at database lock (DBL).

Percentages will be calculated out of the total number of patients in the analysis set displayed in the output, overall and by treatment group.

4.2.1.4 Concomitant medications

All medications will be coded using the latest version of WHO Drug Dictionary (WHODD) available at DBL.

Medications will be classified as:

- Pre-treatment medication: Medications stopped prior to first randomized dose of study medication.
- Prior concomitant medication:
 - Controlled assessment period: Medications started prior to and that continue past the first randomized dose of study medication.
 - Extension period: Medications started prior to the first EQW dose at Visit 7 (Week 24), that either stop or are ongoing in the extension period, continuing past Visit 7 (Week 24). Note, for patients receiving EQW during the controlled assessment period, this definition includes medications started during the controlled assessment period, prior to the first EQW dose at Visit 7 (Week 24) and continuing past Visit 7 (Week 24). These medications will be considered as "new concomitant" for the controlled assessment period in the tabulation of new concomitant medications (see below).
- New concomitant medication:
 - Controlled assessment period: Medications with a start date on or after the first randomized dose up to but not including Visit 7 (Week 24) for patients who enter the extension period. For patients who do not enter the extension period, medications initiated with a start date on or after the first randomized dose up to and including last dose of randomized study medication + 7 days. Hence, for patients who go into the extension period, any medications started on the date of the first open-label EQW dose will be assigned to the extension period.
 - Extension period: Medications with start date on or after Visit 7 (Week 24) up to and including last dose of open-label EQW + 7 days.
- Post-treatment medications: Medications that started the day after the last dose of study medication + 7 days. If the patient discontinues prior to Week 24, the last dose is the last dose of randomized study medication. If the patient discontinues during the extension period, the last dose is the last dose of open-label EQW.

The number and percentage of patients receiving prior concomitant and new concomitant medications will be summarized by treatment and Anatomical Therapeutic Chemical (ATC)

classification (level 4) for the ITT analysis set. The summary will be presented by study period (controlled assessment period and extension period).

Antidiabetic concomitant medications will be summarized separately by chemical/pharmacological/therapeutic subgroup (ATC level 4) and generic term in the same manner.

Background insulin therapy use during the study will be summarized as outlined in Section 3.6.5 for long-acting, short-acting and overall total daily insulin dose. Data collected after discontinuation of study medication will be excluded.

Rescue medications will be summarized during the controlled assessment period for the ITT analysis set and separately during the extension period separately for the subset of ITT patients who received open-label EQW.

A listing for rescue medications will be provided.

Pre-treatment medications and post-treatment medications will be summarized separately by treatment and ATC classification for the ITT analysis set.

Medications with start/stop dates that are partially/completely missing will be imputed as described in [Appendix B2](#).

4.2.2 Overall compliance and extent of exposure

Treatment compliance (number of doses received relative to doses planned) will be summarized by treatment for the safety analysis set.

For the calculation of the compliance, the number of planned doses is defined as the duration of treatment exposure (in days) / 7, rounded to the highest integer.

Compliance will be presented for patients in the controlled assessment period (Week 0 to Week 24) for the Safety analysis set. It will also be presented for the Treatment period (see Section 4.1.1) in the subset of Safety patients who received open-label EQW. For this summary, PBO compliance will be calculated based on EQW exposure. Treatment compliance for controlled assessment period of 24 weeks will be calculated for each patient using the total number of doses received divided by the number of planned doses. Treatment compliance for the Treatment period will be calculated for each patient using the total number of EQW doses received divided by the number of planned EQW doses. Percent compliance will then be categorized to <80%, 80% to <120%, and \geq 120% and summarized by treatment group.

The total number of doses received will be calculated as the total number of used/ partially used vials returned, based on returned used/unused study medication data collected in the eCRF page at each visit.

The total number of medication packets dispensed will be calculated from the study medication dispensation information collected on the DA eCRF.

Exposure will be presented for patients in the controlled assessment period (Week 0 to Week 24) for the Safety analysis set. Separately, it will be summarized for the subset of Safety patients who received open-label EQW for the Treatment period based on EQW exposure.

The following will be used to calculate the duration of exposure, in days:

- Duration of EQW exposure for EQW patients during the Treatment period = Date of Last Injection of Study Medication - Date of First Injection of Study Medication + 7;
- Duration of EQW exposure for PBO patients who enter the extension period = Date of Last Injection of EQW - Date of First Injection of EQW + 7;
- Duration of PBO/EQW exposure during the controlled assessment period = Date of Last Injection of Study Medication during the controlled assessment period - Date of First Injection of Study Medication during the controlled assessment period + 7

Dose interruptions will not be taken into consideration for calculation of duration of exposure.

The mean, SD, median, minimum, and maximum duration of exposure will be provided by treatment group. Extent of exposure will also be categorized into fixed intervals as follows, with number of patients and percentage summarized by treatment group:

- For the summary of exposure during the controlled assessment period, intervals are defined: 1-13, 14-27, 28-55, 56-83, 84-111, 112-139, 140-167, ≥ 168 days
- For the summary of exposure during the treatment period, intervals are defined: 1-13, 14-27, 28-55, 56-83, 84-111, 112-139, 140-167, 168-195, 196-223, 224-251, 252-279, 280-307, 308-335, 336-363, ≥ 364 days

In addition, the extent of exposure will also be summarized by country for both the controlled assessment period and the Treatment period.

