5.5.1.2 Dual chamber pen

Table 3 Identity of investigational product delivered via dual chamber pen

Investigational product	Dosage form and strength	Manufacturer
Exenatide once weekly (EQW)	2.0 mg powder and solvent for prolonged release suspension for injection, prefilled pen ^b	AstraZeneca ^a
Placebo to match exenatide once weekly	Placebo powder and solvent for suspension for injection, prefilled pen ^c	AstraZeneca ^a

^a Responsible for supply of Investigational Product and placebo.

^b Dosage form and strength for non-US sites. For sites in the US only, dosage form and strength are as follows:
Extended release for injectable suspension (2 mg of exenatide per 0.65 mL suspension) in a single dose pen.

^c Dosage form and strength for non-US sites. For sites in the US only, dosage form and strength are as follows:
Placebo powder and solvent for injectable suspension in a single dose pen.

All study medication sufficient for 4-weeks treatment will be packed into patient kits. The prefilled single use injection pens containing the exenatide/placebo will first be individually packed into blister packages and then packed into a box containing 4 prefilled pens.

Study materials will be provided to patients by the Investigator or medically qualified subinvestigator named on Form FDA 1572, or other qualified study-site personnel. Under no circumstance will the Investigator or subinvestigators allow the study medication to be used other than as directed by the protocol or to be administered to any persons other than patients participating in the study. Medically-qualified staff members will be responsible for instructing patients/caregivers on the preparation and administration of the correct doses of study medication.

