12.4 Treatment compliance

Treatment compliance (number of doses received relative to doses planned) will be summarized by treatment for the ITT Population.

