4.2.4.2 Injection-site reactions

Proportions of patients reporting different injection site reactions at Visit 3 (Week 4) through Visit 10 (Week 52).

Injection-site reactions will be identified from the AE dataset using the higher-level term (HLT) “Injection site reactions”. Injection-site reactions reported on the INJECT eCRF will not be included in summaries as this eCRF was introduced part-way through the study and therefore does not provide a complete picture of the number of injection-site reactions. Data reported on the INJECT form will be listed only.

The number and percentage of patients reporting different injection site reactions, per the AE dataset, will be summarized by visit (see Section 4.3.3 for details on visit windows for injection site reactions). This will be provided separately for both the Safety analysis set during the controlled assessment period and for the subset of Safety patients who received open-label EQW during the extension period for the Treatment period. The injection site reactions will be additionally repeated by injection device type i.e. pre-filled syringe or dual-chamber pen. All patients randomized to the study on or after 12th August 2018 are dispensed dual chamber pen devices.

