5. CHANGES OF ANALYSIS FROM PROTOCOL

Section 3.1 of the CSP states that patients return to clinical study site at “6-, 10-, and 12-week intervals but in accordance to the study plan, patients return at 6- and 12-week intervals, with a follow-up visit at Week 62. Section 1.2 of the SAP reflects this.

Per CSP Section 12.1, a Per-Protocol (PP) analysis set is defined. However, given the limitations of PP analyses in that they lead to lack of preservation of the randomization and given the CSP states that efficacy analyses will be carried out on the Evaluable Population “and/or” the Per-Protocol population, i.e. allowing some flexibility, the team agrees to not define a PP analysis set. Additionally, an All Patients analysis set, Randomized analysis set and PK analysis set.

CSP Section 12.1 states that safety will be assessed using the ITT population, however, the team decided a safety analysis set should be defined instead. Patients would be analyzed in accordance to actual treatment received.

CSP Section 12.1 states the Evaluable population will consist of all ITT patients who receive at least 1 dose of study medication and have at least 1 post-baseline HbA1c assessment. It was decided that this definition should be modified to include at least 1 baseline and post-baseline HbA1c assessment.

CSP Section 12.2 has change in C-peptide from baseline to each study week as a secondary endpoint but this was only collected at screening and then for patients in the mixed meal sub-study at Week 52 and Week 62. Therefore this endpoint has been omitted from the SAP.

CSP section 12.2 lists the proportion of patients achieving HbA1c goals of $\leq 6.5\%$ and $< 7.0\%$ as a secondary endpoint. To align with other exenatide studies the addition of goal $< 6.5\%$ has been added.

CSP Section 12.3 states that demographic and baseline characteristics will be summarized for the ITT and Evaluable analysis sets, however the study team requested these be summarized for the ITT and Safety analysis sets.

CSP Section 12.4 states that treatment compliance will be summarized for the ITT analysis set, however, this will be summarized for the Safety analysis set.

A hierarchical testing strategy was not defined in the CSP but has been included in the SAP to protect the family-wise error rate for the primary and secondary endpoints.

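### The SAP 4.2.2 compliance measure ends planned doses at the patient's own last injection, rounds them up, and defines received doses only as vials although later patients use pens

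*SAP*

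**What the plan says.** Protocol 12.4 states the measure in one sentence: "Treatment compliance (number of doses received relative to doses planned) will be summarized by treatment for the ITT Population". It gives neither a planned number nor a data source.

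SAP 4.2.2 makes it operational:

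- **Denominator.** "the number of planned doses is defined as the duration of treatment exposure (in days) / 7, rounded to the highest integer". For the controlled period the exposure formula begins "Duration of PBO/EQW exposure during the controlled assessment period = Date of Last Injection of Study Medication during the controlled assessment period", from which the first injection date is subtracted and 7 days are added. The same section says that interruptions are not deducted.
- **Numerator.** "The total number of doses received will be calculated as the total number of used/ partially used vials returned", with the source given as "based on returned used/unused study medication data collected in the eCRF page at each visit".
- **Presentation.** Percent compliance is grouped as <80%, 80% to <120% and ≥120%. It is shown by treatment group for the controlled period and, in patients who received open-label EQW, for the Treatment period.

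On devices, SAP 4.2.4.2 says "All patients randomized to the study on or after 12th August 2018 are dispensed dual chamber pen devices". Protocol 5.5.1.2 describes that presentation: "The prefilled single use injection pens containing the exenatide/placebo will first be individually packed into blister packages", boxed in fours. There is no separate vial.

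In SAP Section 5 the compliance entry begins "CSP Section 12.4 states that treatment compliance will be summarized for the ITT analysis set" and replaces that set with the Safety set. It mentions nothing else about compliance. Protocol 5.7 separately requires study drug administration to be recorded in the CRF.

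**The concern.** The measure is described as received relative to planned, but the planned count comes from what the patient did, not from the schedule. Two patients with the same intake can then fall in different compliance categories, depending only on when they missed doses. Rounding up treats a dose given inside the permitted window as if a further dose had been due. The numerator names a container that pen users do not have.

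What is at stake is whether the compliance table means what its label says, in particular its <80% category, and whether the syringe and pen cohorts are counted on the same basis.

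**Working it through.** **Inputs**

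- Exposure D = last injection − first injection + 7 days; planned doses P = D/7 rounded up; compliance = used units returned / P (SAP 4.2.2).
- Scheduled controlled-period doses: weekly at Weeks 0 to 23, so 24. The note to Figure 1 in SAP 1.2 makes the Week 24 dose open-label.
- Dosing window: ±2 days relative to the first dose (Protocol 5.5.2).

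**Check against the plan's own figures.** The documents state no compliance percentage, but SAP 4.2.2 gives top exposure bands from the same duration formula. For 24 exactly weekly doses, D = 23×7 + 7 = 168 days and P = 24. For 52, D = 51×7 + 7 = 364 days and P = 52. These match the bands ≥168 and ≥364 days.

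**Step 1: the denominator.** Assume the last injection is on its nominal day and all units are returned.

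| Pattern | D (days) | P | SAP score | Against 24 |
|---|---|---|---|---|
| 6 doses, then stop | 5×7+7 = 42 | 6 | 6/6 = 100% | 6/24 = 25% |
| 12 doses, then stop | 11×7+7 = 84 | 12 | 12/12 = 100% | 12/24 = 50% |
| 18 doses, last six missed | 17×7+7 = 126 | 18 | 18/18 = 100% | 18/24 = 75% |
| 18 doses, six in the middle missed | 23×7+7 = 168 | 24 | 18/24 = 75% | 18/24 = 75% |
| 12-week span, three missed before the last dose | 84 | 12 | 9/12 = 75% | 9/24 = 37.5% |

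Rows three and four have the same intake but fall on opposite sides of 80%. The last row shows that doses missed before the last injection do count.

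**Step 2: rounding.** For a full course with the last dose one day late, D = 169, 169/7 = 24.14 and P = 25, so the score is 24/25 = 96.0%. Two days late gives 170/7 = 24.29 and again P = 25. In general, k doses (k ≥ 2) with none missed and an in-window late last dose score k/(k+1):

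- k = 2: 2/3 = 66.7%
- k = 3: 3/4 = 75.0%
- k = 4: 4/5 = 80.0%
- k = 6: 6/7 = 85.7%
- k = 12: 12/13 = 92.3%

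Only k = 2 and k = 3 fall below 80%. An early last dose changes nothing: 166/7 = 23.71, P = 24.

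**Step 3: the numerator.** A pen user with 24 doses has no vials. The literal score is 0/24 = 0%; counting pens gives 24/24 = 100%. Unreturned units also matter: a 12-week span with no missed dose but 10 of 12 units returned scores 10/12 = 83.3%.

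**The case against.** The strongest reply is that this is a coherent on-treatment measure. The primary estimand excludes data after discontinuation of study medication (SAP 4.2.3.1), so adherence while on treatment is a sensible companion to it. A fixed denominator of 24 would mix stopping for any reason, including adverse events, with poor adherence. Early stopping is reported by arm in disposition (SAP 4.2.1.1) and in the exposure bands (SAP 4.2.2). Compliance enters no efficacy model, and SAP Section 5 drops the per-protocol set. All of this stands, and it makes replacing the denominator outright partly a matter of preference. It does not answer the missing on-treatment label, the rounding, or the vial-only count.

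Several stronger readings are tempting, but the documents do not support them:

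- **Early stoppers, or most drop-outs, score 100%.** This needs no earlier missed dose, every unit returned, and a last dose no later than its nominal day. The documents give no data on any of these.
- **Pen users have no countable doses.** The 0% follows from the wording alone. The named source is returned study medication in general, pens are single-use and can be counted, and administrations go into the CRF. Vial wording also remains in Protocol Table 4 and Protocol 5.7.1.
- **A perfect completer has 25 planned doses because the controlled period includes the Week 24 date.** SAP 3.6.5.2 ends the period on that date for most safety parameters so that pre-dose assessments fall inside it. SAP 1.2 makes that injection open-label, and the 168-day band fits 24 doses.
- **Section 5 hides a departure from the protocol.** Protocol 12.4 does not define planned doses, so there is no clear departure to declare.
- **A reader could not tell whether a weak HbA1c effect reflects poor adherence.** This would hold only if the compliance table were read without the exposure and disposition tables.

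**Conclusion.** The point holds for one descriptive table. As written, SAP 4.2.2 makes the score depend on when doses were missed as well as how many (100% against 75% for the same 18 of 24 doses). It charges an extra planned dose for a last injection 1 or 2 days late within the window (96% for a full course; below 80% only at 2 or 3 doses). Read literally, it counts no doses for anyone on the pen.

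The percentages assume on-time dosing and full return of units except where stated. The size of the pen cohort is not given, so the effect on the reported <80% category cannot be estimated. No efficacy result is affected.

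**What to change.** In SAP 4.2.2:

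1. Define a received dose as a used vial or a used pen, or take it from the CRF administration records. State how unreturned units are handled.
2. Round so that an in-window late last dose adds no planned dose. Rounding to the nearest integer would do this: 169/7 = 24.14 and 170/7 = 24.29 both give 24, as does an early 166/7 = 23.71.
3. Label the current measure as on-treatment compliance, and add a line against the protocol schedule: 24 doses for the controlled period and, for EQW over the Treatment period, 52 doses (24 + 28) or 28 for placebo-to-EQW patients. The extension kits in Protocol Table 4 supply (1+3+3)×4 = 28 doses. However, Protocol 3.1 and SAP 1.2 place the last dose at Visit 10 (Week 52), which counted from Week 24 would be a 29th. Those passages should be reconciled before the count is fixed.
4. Correct the cross-reference for the Treatment period from Section 4.1.1 to Section 3.6.5, and note the added line in Section 5 for transparency.

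The cost is SAP wording and slightly more programming on data already collected. The schedule-based figure will be lower than the on-treatment one and will combine discontinuation with missed doses, so the two lines should be shown together.
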